# 3.2 Study Outcome Measures

# 3.2.1 Primary

The rate of PrEP uptake will be assessed during follow-up by self-report at months 3, 6, 9, and 12. Self-report will be confirmed by laboratory testing for the presence of tenofovir diphosphate (TFV-DP) and/or photograph of PrEP prescription or bottle.

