#### 4 STUDY DESIGN

We will conduct a randomized controlled trial (RCT) with two arms. Participants in the intervention arm will receive access to the HealthMindr app with basic prevention services (HIV test planning and test locators; risk assessment; HIV treatment locators; and condom, HIV test kit, and at-home STI specimen collection kit distribution) plus monthly PrEP eligibility assessments, PrEP provider locator, enhanced information about PrEP, and referrals to local PrEP navigators. The app also provides links to health insurance exchanges, where men can seek health insurance (all cities) or payment assistance programs. The control arm will be standard of care (receive baseline survey, followed by referral to existing online PrEP and HIV prevention information; with a mobile-phone administered attention control survey about diet and exercise (and PrEP initiation) of the same length as the monthly PrEP assessment given to the intervention arm, to maintain the same monthly frequency of contact with control participants. Control arm participants will not have access to the active app.

Study participants are followed for 12 months with outcome measurements occurring in both arms at 3-month intervals and monthly brief surveys to assess PrEP uptake and reassess PrEP eligibility (intervention arm) or assess diet and exercise (control arm). Surveys will be distributed to all participants through the mobile app at baseline and quarterly. Participants will specify their preference for communication media in the baseline survey. Quarterly surveys will last approximately 30 minutes; to limit survey duration, some non-labile survey elements will not be assessed at each time point. Quarterly surveys are identical for men in both arms, except the final survey includes questions on acceptability only for men who used the app. Surveys are smartphone-optimized so that they may be completed on participants' phones. The survey

measures represent a comprehensive set of previously validated measures that will characterize the population, allow for assessment of adequacy of randomization, document important outcomes, and allow for exploration of possible moderating factors. A summary of measures is included in Figure 2.

Figure 2. Measures to be assessed in participant surveys.

Outcomes	Community & Network Characteristics
PrEP Awareness/Use/Efficacy	Health Care Environment
Participant has heard of PrEP	Payer source: insurance coverage, out-of-pocket

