# 5.2.3 Participant Compensation

Compensation for survey completion will be graduated (\$50 baseline, \$40 months 3 and 6, \$50 month 9, \$60 month 12). Study incentives for the baseline will be sent 48-72 hours after completion of the baseline survey to allow for review of data and identification of possible fraudulent or duplicate enrollments. Incentives for IDIs and quarterly follow-up surveys will be processed electronically at the time of interview or survey completion (see Fraud Deterrence). Men in both arms will be asked monthly if they have initiated PrEP; men who report initiating PrEP in either arm will be mailed a dried blood spot collection kit with instructions and a prepaid return mailing envelope, and will be directed to collect and mail a dried blood spot specimen for tenofovir diphosphate detection. Those who return a DBS specimen will be provided with an additional compensation of \$40. Participants will also be asked to take a picture of their prescription or PrEP label; those who provide a photograph will be provided with an additional compensation of \$15. A maximum compensation of \$295 could be provided for completing all of the study visits (\$240), DBS specimen (\$40), and PrEP prescription photo verification (\$15).

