# 5.3 Treatment Assignment Procedures

#### 5.3.1 Randomization Procedures

After providing informed consent, downloading the study application, and passing the fraud check, participants will be randomized to study arms in a 2:1 ratio of intervention to control arms (rationale: to allow sufficient data on app users to allow for analysis of efficacy by level of app usage), stratified by MSA to ensure balance of the study arms across the three study sites. Within each city stratum, a computer program will randomly assign each participant to the next treatment allocation from a random-permuted block randomized sequence. Once participants are randomized, they will be kept in and analyzed according to their original assignment (i.e., intent-to-treat). Participants who are not verified as legitimate or are unable to download the app will not be randomized into the study.

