# 7.3 Follow-up Visits

All participants will be asked to complete quarterly surveys through the app for follow-up visits at Month 3, 6, 9 and 12. Participants who have indicated starting PrEP will be asked to upload a picture of their prescription and/or be asked to self-collect DBS using a home test kit.

Both groups will also receive a monthly assessment. The intervention group will receive a monthly PrEP assessment and the Control group will receive a survey about diet and exercise of similar length. All participants will also be asked questions to ascertain whether they started PrEP within the past month. Generic questions about new medication prescriptions will be used in the control arm so that PrEP is not mentioned specifically. Intervention arm participants will be asked if they have initiated PrEP prior to starting the monthly PrEP assessment. Participants reporting PrEP initiation will then complete a PrEP adherence assessment.

The intervention group will be able to use the resources in the app throughout the study, including placing orders for home test kits, condoms and lubricant.

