#### 12.2 Sample Size Considerations

Power calculations were conducted for the main analysis of time to PrEP initiation comparing the intervention arm with the control condition. Current estimates of PrEP uptake in the most recent 4 quarters for which data are available are that 4,507 men started PrEP $^{50}$ . Assuming all of these men are MSM, which is an overestimate, and using as the denominator the number of MSM estimated by CDC to be eligible for PrEP22, only 4,507/492,000 = 0.9% of eligible MSM started PrEP between mid-2104 and mid-2015. Thus, our assumption that at most 2% of men in the control arm will initiate PrEP during the study period is conservative. Based on our preliminary pilot data, men using the app initiated at 9% per 4 month period; we conservatively estimate that men in the intervention period would initiate PrEP at 9% in a year. We propose a total sample size of 438 intervention arm and 219 control which will provide 91% power ( $\alpha = 0.05$ ) to detect a 4.5 fold increase in the hazard of uptake in the intervention arm compared to the control arm. If our effect were less than our conservative estimates, we would retain reasonable power (4-fold: 80% power; 3.5-fold: 74% power). These power calculations assume 20% annual attrition.

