#### 12.3 Final Analysis Plan

The main analysis will use four standard survival analysis techniques to compare the rate of PrEP initiation by study arm and estimate the size and statistical significance for observed differences. This approach will account for loss-to-follow-up, study termination due to competing events (e.g., HIV seroconversion), and other forms of censoring. The first analysis will use Kaplan-Meier methods to characterize the empirical survival distribution, which here is the timedependent probability of remaining PrEP uninitiated over follow-up. This method will yield estimates of the median time to PrEP initiation and cumulative incidence with 95% confidence intervals. Second, log-rank or related (e.g., Harrington-Fleming) statistical tests will be used to test the null hypothesis of no difference in rates of PrEP initiation by study arm, with a cutoff p value of 0.05 used to determine significance. 52 Third, a Cox proportional hazards model will be used to estimate the hazard ratio associated with study arm to characterize the strength of causal effect of use of the app. The primary model will only include an independent exposure variable for the study arm as randomized (i.e., standard intent-to-treat analysis), but secondary models may include covariates (including those related to the four domains along the PrEP continuum) for which there is descriptive evidence of residual imbalance after randomization. Fourth, parametric survival models (e.g., under exponential or Weibull distributional assumptions) will be used to characterize the rate of PrEP initiation overall and by study arm.

Mediation Analysis: This analysis will examine how study arm assignment may lead to intermediate effects, such as greater access to HIV testing or decreased risk behavior, which themselves are associated with the primary effect of PrEP initiation. Using the difference method for a set of Cox proportional hazards models similar to those in the Aim 2 analyses, log coefficients for the indirect effects will be subtracted from log coefficients for the direct effect to estimate the size of the mediation. Mediators will be selected on the variables known to be associated with the 4 domains of the PrEP continuum (including awareness, access, and engagement with HIV prevention services), and changes in risk behaviors resulting from app utilization.

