# 14.1 Recontacting Past Participants

Participants who reported PrEP initiation on a monthly check-in survey but not a quarterly survey (primary study outcome) will be contacted for clarification. Only the participants who previously provided consent to be recontacted will receive a message. A \$20 compensation in the form of electronic gift code will be given to those participants who respond.

Voicemail: Hi, this is [insert your name] calling from Emory with the HealthMindr study. You have reported starting PrEP during our research study, but you also reported that you have not started PrEP in surveys afterwards. I was hoping to verify some information from your time in the study. You are eligible to receive additional compensation for your response. You can call us back at [phone number]. Or feel free to text me and let me know what the best time is for a call. Thank you!

Phone Script: Hello, may I speak with [PARTICIPANT'S NAME]? My name is [insert your name]. I am with Emory working on the HealthMindr study. You have reported starting PrEP during our research study, but you also reported that you have not started PrEP in surveys afterwards. According to your survey, you reported PrEP usage in [MONTH/YEAR]. Is this correct? Did you stop taking PrEP any time after?Thank you for your clarification. Also for the compensation, we will send you a \$20 gift code. Do you have a preferred store? We have gift codes from Amazon, Target and Walmart.That is all the questions I have and thank you for participating in our research study!

Text Message: Hello! This is [NAME] from the Emory HealthMindr study. We were hoping to get you on a call for a few minutes to to verify some information from your time in the study and you will be compensated for your time. What time works best for you for a short phone call?

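### Section 12.3 does not fix the one test that carries the 0.05 decision, and its primary model leaves out the MSA strata used in randomisation

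*Combined protocol and SAP*

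**What the plan says.** **Test.** Section 12.3 lists four survival techniques and puts the significance decision on the second: "log-rank or related (e.g., Harrington-Fleming) statistical tests will be used to test the null hypothesis of no difference". It gives the level as 0.05. It does not name one test, the weights, the sidedness, or when the choice is made.

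**Model.** The primary Cox model in the same section contains arm and nothing else. Section 5.3.1 says allocation is "stratified by MSA to ensure balance of the study arms across the three study sites". No stratified test or model is specified. The number of strata is not settled either: section 4.1 names 5 locations that may be added to the three sites, and section 5.2.1 names 16.

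**Power.** Section 12.2 gives 91% power with 438 and 219 men "to detect a 4.5 fold increase in the hazard of uptake in the intervention arm compared to the control arm", allowing for 20% annual attrition.

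**Timing.** Section 3.2.1: "The rate of PrEP uptake will be assessed during follow-up by self-report at months 3, 6, 9, and 12". Section 14.1 deals with men who reported a start on a "monthly check-in survey but not a quarterly survey (primary study outcome"). Section 4 adds that "Quarterly surveys are identical for men in both arms", apart from acceptability items in the last one. Monthly reports are collected as well: "Men in both arms will be asked monthly if they have initiated PrEP" (section 5.2.3) and "All participants will also be asked questions to ascertain whether they started PrEP within the past month" (section 7.3).

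**The concern.** The sentence that decides whether the trial succeeds admits a family of tests. If the member is picked in advance, each one holds its level. If it is picked after the results are known, the true error rate depends on how far the candidate tests can disagree. The choice of weights would also change the power that the sample size was meant to secure. Leaving out the randomisation strata raises a separate, smaller question: whether the analysis matches the design, and whether that costs anything.

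**Working it through.** **1. The plan's own figure.** Inputs from section 12.2: 2% and 9% initiation in a year, 219 and 438 men, 20% loss. Take 0.8 × 219 = 175.2 and 0.8 × 438 = 350.4 men, two-sided 0.05, comparing two proportions.
- Pooled risk: (0.02 + 2 × 0.09)/3 = 0.0667.
- Null SE: √[0.0667 × 0.9333 × (1/175.2 + 1/350.4)] = 0.0231.
- Alternative SE: √[0.02 × 0.98/175.2 + 0.09 × 0.91/350.4] = 0.0186.
- z = (0.07 − 1.96 × 0.0231)/0.0186 = 1.33, so power is 90.9%.

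The 91% reproduces, as it does for a simulated log-rank test on 350 and 175 men (91.0%). One-sided, the same formula gives 95.8%, so two-sided is the natural reading. Treating attrition as exponential censoring of all 657 men gives about 93.9% for log-rank. The comparisons below start from that figure and should not be set against 91%.

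**2. Why early weights are harmless and late ones are not.** Harrington-Fleming weights are S^ρ(1 − S)^γ, where S is the pooled proportion not yet initiated just before the event. Under the null, the correlation of a weighted test with log-rank is approximately E[w]/√E[w²], taken over events. The planned pooled uptake is (438 × 0.09 + 219 × 0.02)/657 = 6.7%.
- Early (1,0): the weight falls only from 1 to 0.933. With events spread evenly, the correlation is 0.9667/√0.9348 = 0.9998.
- Late (0,1), exact dates: the weight rises from 0 almost in proportion to time. Correlation 0.5/√(1/3) = 0.866.
- Late (0,1), quarterly times: weights in the ratio 0, 1, 2, 3, so month-3 events count for nothing. Correlation 1.5/√3.5 = 0.80.

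For two standard normal statistics, the chance that at least one exceeds 1.96 in absolute value is 5.2% at correlation 0.999, 7.3% at 0.866, 7.8% at 0.80 and 8.0% at 0.765. Simulated late-weight correlations were 0.77 to 0.86.

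**3. Type I error by simulation** (438 and 219 men, exponential times, 20% attrition).
- Log-rank or (1,0): 4.5% to 5.4% at 2% to 9% uptake. The two agreed in at least 99.6% of trials.
- Log-rank or (0,1): 7.3% to 8.1% at 6.7% uptake, 7.5% to 8.0% at 9%, and 6.3% to 7.1% at 2%, where each test alone is conservative. One quarterly run at 6.7% gave 8.4%, but its single tests ran at 5.2% to 5.4%; it should not be relied on.

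**4. Power, control risk 2%** (10,000 replicates, SE at most 0.5 point).

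| Hazard ratio, times | Log-rank | (1,0) | (0,1) |
|---|---|---|---|
| 4.5, exact | 93.8% | 93.8% | 83.7% |
| 4.5, monthly | 93.8% | 93.8% | 81.9% |
| 4.5, quarterly | 93.9% | 93.9% | 76.5% |
| 3.5, exact | 76.5% | 76.5% | 60.8% |
| 3.5, quarterly | 76.6% | 76.7% | 51.9% |

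At 4.5 the late weight loses 93.8 − 83.7 = 10.1 points with exact dates and 93.9 − 76.5 = 17.4 with quarterly times.

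**5. Dropout within a quarter.** The quarterly log-rank figures above keep events that occur before a missed survey. If those events are lost, log-rank power at hazard ratio 3.5 falls from 75.9% to 73.5% in one run and from 76.4% to 74.6% in another: about 2 points.

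**6. Strata** (MSA sizes and rates are assumptions).
- Three MSAs, equal rates: 95.3% with or without strata (2% against 9%).
- Control risks 1/2/3%, hazard ratio 4.5: 93.8% unstratified, 93.9% stratified.
- Control risks 0.5/1.5/4%, hazard ratio 3.5: 74.1% and 74.9%; type I error 4.2% to 4.3% unstratified, 4.7% stratified.
- Control risks 5/10/20%, well above plan, hazard ratio 1.8: 70.7% and 72.3%.
- Nineteen MSAs (16 added, 2 to 26 men each), equal rates, hazard ratio 3.5, exact dates: 76.6% unstratified, 76.1% with all 19 strata, 76.2% with MSAs under 30 men pooled. With unequal risks: 74.2%, 74.3% and 74.8%. Type I error with pooling was 5.0%.

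**The case against.** The context points to log-rank. Section 12.3 names it first, section 12.2 powers on a hazard ratio, and the score test of an arm-only Cox model is the log-rank test. A late-weighted success without log-rank support would normally sit beside a Cox interval that includes or nearly touches 1, so it would be hard to conceal. The plan never mentions late weights, and whether the source it cites for the test family covers them cannot be checked from the documents. All of this stands. It makes log-rank the likely intention and late weighting the less likely reading. It does not turn the sentence into a commitment.

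A reader might infer that the plan as written runs at 7% to 8% type I error. It does not. That figure needs late weights and a choice made after seeing the data, and the documents state neither.

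A reader might also infer that the event time scale is undefined. Sections 3.2.1, 4 and 14.1 largely settle it as quarterly. What is missing is the date given to an event within a quarter and the treatment of men who drop out before the next survey.

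On strata, the objection that the gain is slight is correct, and with many small strata there can be a small loss.

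**Conclusion.** The point holds as a gap in specification. The test behind the 0.05 decision is not fixed, and the primary model does not use the factor by which men were randomised.
- **Early weights:** no practical effect at the planned uptake.
- **Late weights chosen after seeing the data:** about 7% to 8% type I error in the worst case, slightly less at 2% uptake.
- **A late-weighted primary test:** about 10 points of power lost with exact dates and 17 with quarterly times, at a hazard ratio of 4.5.
- **Strata:** a gain of about one point of power when MSA rates differ, none when they are equal, and up to about half a point lost with many small strata.

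It would be wrong to read the missing strata as invalidating the result: the arm-only test kept its level in every setting tried and was slightly conservative when MSAs differed. It would also be wrong to call quarterly timing free, given the loss of about 2 points under one dropout rule. The figures assume exponential initiation and dropout, proportional hazards, and the assumed MSA sizes and risks.

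**What to change.** Before any outcome is tabulated by arm, amend section 12.3 as follows.
- Name one primary test: the two-sided 0.05 log-rank test stratified by randomisation MSA.
- Report the Cox hazard ratio stratified by the same factor, with a stated method for ties, and describe it as a within-MSA hazard ratio.
- Because sections 4.1 and 5.2.1 allow added locations, set a pooling rule in advance, blind to arm and outcome. For example: any MSA with fewer than 30 men randomised at close of enrolment joins one pooled stratum; if that stratum has fewer than 30 men, it merges with the smallest remaining MSA. A threshold of 12 changed simulated power by at most 0.2 point.
- State how an event is dated within a quarter, and how an event is counted when the man drops out before the next survey.
- Keep the arm-only Cox model and any weighted test, with its weights written down, as sensitivity analyses.

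The cost is SAP wording. MSA is already a randomisation field, so no new data, men or procedures are needed. The one substantive change is that the main hazard ratio becomes a within-MSA quantity; the arm-only model remains for comparison.

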# **PROTOCOL SUMMARY**

Title:	HealthMindr: Theoretically based mobile app to increase PrEP uptake among MSM
Précis:	The study is based on the premise that providing, through a mobile phone app, self-directed PrEP information; periodic PrEP eligibility screenings to identify risk and eligibility objectively; referral to PrEP providers with directions; and related prevention services will increase the uptake of PrEP among at risk, HIV-negative MSM to a greater extent than standard of care referrals to existing resources.
Objectives:	Aim 1: Test an HIV prevention mobile app versus a standard of care condition with outcome of rate of PrEP uptake among MSM.
	Aim 2: Quantify the behavioral, social, and clinical factors that mediate and moderate the efficacy of the HealthMindr app on the rate of PrEP uptake.
	Aim 3: Conduct individual in-depth interviews (IDIs) to assess how the app promoted PrEP uptake, unmet needs of men who did not start PrEP, and how repeated app interactions might further PrEP uptake.
Population:	680 MSM, aged 18-34
Sites:	Atlanta, GA; Jackson, MS; and Washington, DC
Intervention:	HIV prevention mobile app with basic prevention services including HIV test planning and test locators; risk assessment; HIV treatment locators; and condom, HIV test kit, and at-home STI specimen collection kit distribution plus monthly PrEP eligibility assessments, PrEP provider locator, enhanced information about PREP, and referrals to local PrEP navigators.
Study Duration:	60 months
Subject Participation Duration:	12 months
Estimated Time to Complete Enrollment:	18 months

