### 3.2.2 Secondary

Mediation Analysis: This analysis will examine how study arm assignment may lead to intermediate effects, such as greater access to HIV testing or decreased risk behavior, which themselves are associated with the primary effect of PrEP initiation. Using the difference method for a set of Cox proportional hazards models, log coefficients for the indirect effects will be subtracted from log coefficients for the direct effect to estimate the size of the mediation.  Mediators will be selected on the variables known to be associated with the 4 domains of the PrEP continuum (including awareness, access, and engagement with HIV prevention services), and changes in risk behaviors resulting from app utilization.

Moderation Analysis: This analysis will examine how attitudes and beliefs about PrEP, as well as individual, social, and community characteristics can moderate the effect of the app on PrEP initiation. Examples of moderators include perceived benefits of PrEP use, self-assessed vulnerability to HIV, perceived advantages to meeting partners if currently taking PrEP, and social support for PrEP use within one's social network.

Demographic factors including age, race/ethnicity, and geographic setting will also be critical moderators. Although the distribution of these factors will be balanced across study arm with randomization, they may have effects on the level of engagement in the app (i.e., post-randomization treatment adherence) that itself will influence the rate of PrEP initiation. Given this causal model, we will use instrumental variable analyses to estimate the effect of optimal app use on PrEP initiation given measured and unmeasured moderators.

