#### 12 STATISTICAL CONSIDERATIONS

# 12.1 Study Hypotheses

- 1) The rate of PrEP uptake will be higher among men provided with the HealthMindr app compared to men provided with standard of care.
- 2) Access to additional HIV prevention services available in the HealthMindr app will result in reductions in risk behaviors or greater access to HIV testing services, which are associated with PrEP uptake.
- 3) Individual, social, and community characteristics of participants will be associated with PrEP uptake among participants provided access to the HealthMindr app.

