#### 15 ETHICS/PROTECTION OF HUMAN SUBJECTS

#### 15.1 Potential Risks and Benefits

#### 15.1.1 Potential Risks

The potential risks to participants are minimal.

Surveys: Some participants may be uncomfortable answering personal questions, or feel uncomfortable with the HIV prevention topics. Men will have the option for all questions to not answer.

Disclosure of participation in a research study: There is a possibility that someone participating in an online data collection could be identified as participating in research, but this is uncommon. There is some risk that those who participate in online surveys could be observed if they complete the surveys in public, or that data could be at risk during transmission. We will mitigate this risk by reminding participants at the beginning of each survey to complete the survey in a private place, where their responses cannot be observed by others. We will also encourage participants to delete any emails or text messages received as part of the study to protect them from an unauthorized individual viewing the messages.

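### The mediation rule names the difference method but writes the subtraction with the wrong terms, and it identifies its Cox models only by a circular pointer to Aim 2

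*Combined protocol and SAP*

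**What the plan says.** The mediation rule appears twice in the combined protocol and SAP, in almost the same words.

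- Section 3.2.2 (Secondary): "Using the difference method for a set of Cox proportional hazards models, log coefficients for the indirect effects will be subtracted", and the sentence goes on to subtract them from the direct-effect coefficients.
- Section 12.3 (Final Analysis Plan): "Using the difference method for a set of Cox proportional hazards models similar to those in the Aim 2 analyses", followed by the same rule, that "log coefficients for the indirect effects will be subtracted from log coefficients for the direct effect to estimate the size of the mediation".

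Both sections say where the mediators come from: the four domains of the PrEP continuum and changes in risk behaviour. Neither mentions a total effect, defines direct or indirect, or says that one model leaves the mediator out and the other includes it.

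Section 12.3 describes two other kinds of Cox model. For the main comparison, "The primary model will only include an independent exposure variable for the study arm as randomized". Beyond that, "secondary models may include covariates (including those related to the four domains along the PrEP continuum) for which there is descriptive evidence of residual imbalance" between the arms. The mediation text refers to neither.

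The Protocol Summary defines the aim in question: "Aim 2: Quantify the behavioral, social, and clinical factors that mediate and moderate the efficacy of the HealthMindr app". The hypothesis behind the mediation analysis is the second one in section 12.1: "Access to additional HIV prevention services available in the HealthMindr app will result in reductions in risk behaviors or greater access to HIV testing services", these being associated with PrEP uptake.

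**The concern.** The indirect effect is the mediated effect. It is what the difference method is meant to produce, not a quantity to subtract from something else. A rule that takes the indirect effect away from the direct effect does not give the size of mediation, and it moves the wrong way: the larger the mediated part, the smaller the result.

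The size of mediation is a stated secondary objective and the quantity that addresses hypothesis 2. An analyst who works from the plan has a method name and a formula that disagree. The model description does not settle the matter, because it refers back to the aim it is supposed to specify. A later reader could not tell from the plan which computation had been prespecified.

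**Working it through.** The documents state no mediation figure, so there is none to reproduce. The check is algebra, with the planning hazard ratios used only to give it a scale.

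**Inputs**

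| Input | Value | Source |
|---|---|---|
| Hazard ratios, intervention against control | 4.5, 4, 3.5 | Section 12.2 |
| Uptake, control and intervention | 2% and 9% | Section 12.2 |
| Allocation | 2:1 | Section 5.3.1 |
| Share of the effect that is mediated, s | 0 to 100% | Assumed; not in the documents |

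**Step 1. The named method.** On the log-hazard scale, T = D + I. T is the arm coefficient from the model without the mediator, and D is the arm coefficient with the mediator added. The difference method gives I = T − D.

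**Step 2. The written rule in standard terms.** D − I = (T − I) − I = T − 2I. With I = sT this is (1 − 2s)T. It equals I only when T = 3I, that is, when exactly one third of the effect is mediated.

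**Step 3. Numbers at a hazard ratio of 4.5**, where T = ln 4.5 = 1.504:

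| Assumed share mediated | D | I = T − D (named method) | D − I (literal rule) |
|---|---|---|---|
| 0% | 1.504 | 0 | 1.504 |
| 25% | 1.128 | 0.376 | 0.752 |
| 50% | 0.752 | 0.752 | 0 |
| 75% | 0.376 | 1.128 | −0.752 |
| 100% | 0 | 1.504 | −1.504 |

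At hazard ratios of 4 and 3.5, T is 1.386 and 1.253 and the pattern only rescales. The literal rule gives 0.693 and 0.626 at 25%, 0 at 50%, and −0.693 and −0.626 at 75%.

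**Step 4. The same rule with the labels swapped.** Suppose direct means the arm coefficient without the mediator (T) and indirect means the arm coefficient with it (D). The subtraction is then T − D = I, which is the difference method, with zero error at every share.

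**Step 5. Does the additive split hold for Cox models at these rates?** It was checked by simulation: 300,000 men, 2:1 allocation, one year of follow-up, event rates of about 1.9% and 8.7%, and an assumed normally distributed mediator. With a true indirect effect of 0.40, the two fitted models gave 1.526 − 1.132 = 0.394, and the literal rule gave 1.132 − 0.394 = 0.738. With a true indirect effect of 0, the difference was −0.009 and the literal rule gave 1.550. The split in Step 1 is therefore a fair approximation here. The simulation says nothing about how precise the estimate would be in this trial.

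**Step 6. Following the pointer to the models.** Section 12.3 describes the mediation models as resembling those of Aim 2. The Protocol Summary says that Aim 2 is mediation and moderation. The pointer leads back to the analysis it is meant to define. The arm-only Cox model earlier in 12.3 is the natural source of T, but the mediation text does not cite it.

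**The case against.** The strongest reply is that the literal rule is not a workable procedure under the method named. The difference method fits two models and compares their arm coefficients. Neither fit yields a coefficient that is the indirect effect; that value exists only once T − D has been computed, and computing D − I would mean subtracting the answer a second time. A product of coefficients could supply I separately, but neither section names that approach. The swapped-label reading is the only one that two fitted models can carry out directly. This stands, and it makes that reading the likely intent. It does not make the text correct. The plan then gives the right answer only if both labels are reinterpreted, and no section does so.

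Three stronger readings are tempting, and the documents do not support them.

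- *The reported mediation will be wrong or reversed in sign.* The errors in the table belong to the literal reading alone and rest on assumed mediated shares. They are not expected errors.
- *No mediator-adjusted model is planned.* The named method and the stated source of mediators imply one. It is under-described, not absent.
- *The two models will be fitted on different men.* The consent-related text says "Men will have the option for all questions to not answer", so some mediator data may be missing. But that is a general statement about surveys. The plan sets no complete-case rule for mediators and gives no skip rate. This is missing detail, not a shown error.

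**Conclusion.** The point holds as a specification error. Both sections name the difference method and then write a formula that contradicts it in standard terms: T − 2I in place of T − D. The cross-reference that should identify the models is circular.

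The numerical size depends on the reading. On the likely intent, the error is zero and only the labels are wrong. On the literal reading, the rule would report the whole effect when nothing is mediated, zero at one half, and a negative value beyond that. Those figures assume the additive split on the log-hazard scale, the planning hazard ratios, and mediated shares that the documents do not give.

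The consequence is limited to the secondary Aim 2 mediation estimate. The primary intention-to-treat comparison and the sample size are not touched. The correction is still worth making before the analysis, because it costs almost nothing and the estimate addresses a stated hypothesis.

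**What to change.** In both 3.2.2 and 12.3, replace the subtraction clause with wording such as: *mediated (indirect) effect = log HR for study arm from the Cox model without the mediator (total effect) minus log HR for study arm from the same Cox model with the mediator added (direct effect)*.

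In 12.3, replace the pointer to Aim 2 with a reference to the arm-only Cox model described earlier in that section.

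The cost is one sentence in each of two sections and one cross-reference, with no new data or visits. Stating that both models are fitted on the same participants would be good practice. It would add up to one refit of the arm-only model per mediator, but the correction does not depend on it.
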